10. COMPLETION AND STOPPING CRITERIA

10.1. Individual Subject Stopping Rules

Participants may be prematurely terminated from the study for the following reasons:

- The participant elects to withdraw consent from all future study activities, including follow-up
- The participant is “lost to follow-up” (i.e., no further follow-up is possible because attempts to reestablish contact with the participant have failed)
- The investigator no longer believes participation is in the best interest of the participant
- The participant dies
- Missing 2 consecutive doses of study drug (dupilumab or placebo)
- The participant does not tolerate 5 mg milk protein at the initial escalation (Visit 4)
- Missing ≥ 7 consecutive days of milk protein OIT therapy (e.g. concurrent illness such as gastroenteritis)
- Anaphylaxis resulting in hypotension, neurological compromise or mechanical ventilation secondary to OIT dosing or any food challenge
- The subject develops biopsy-documented eosinophilic esophagitis (EoE) with synchronous symptoms or other eosinophilic gastrointestinal disease
- Any serious or unexpected adverse event
- Any subject deemed to have severe allergic reactions and who receives aggressive therapy (e.g., mechanical ventilation, three or more doses of epinephrine for a life threatening reaction) at any time should be discontinued from further therapy
- Other circumstances including, but not limited to, the following:
 - Poor control or persistent activation of secondary atopic disease (e.g., AD, asthma)
 - Started on beta-blockers, or other prohibited medications, with no alternative medications per the prescribing clinician
 - Pregnancy

Subjects who are withdrawn prematurely from the study will be asked to complete study assessments, as described in **Section 8.5**.

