10.3. Study Stopping Rules

During the course of the study, if the investigator or DSMB discover conditions that indicate that the study should be discontinued, an appropriate procedure for terminating the study will be instituted, including notification of the FDA and IRB or EC (ethics committee).

If any of the stopping rules listed below are met, study enrollment will be suspended, the initial dose day will be suspended, dose escalation during build-up will be paused, and all enrolled participants will remain on their current dose pending expedited review of all pertinent data:

- Any death related to dosing
- More than one participant requiring more than two injections of epinephrine during a single dupilumab injection

- One case of severe and prolonged anaphylaxis related to milk OIT dosing or oral food challenge that does not respond to 3 doses of epinephrine or that includes intubation
- More than 2 cases of hypotension related to milk OIT or oral food challenge
- More than 3 participants require more than 2 injections of epinephrine for anaphylaxis during a single dosing event of milk OIT
- More than 3 of either of the following events:
 - Severe adverse event, other than anaphylaxis, related to investigational product or
 - Eosinophilic esophagitis with clinical symptoms and confirmatory biopsy findings

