With respect to the inclusion of being “potentially life-threatening” in the definition of anaphylaxis and how that relates to the assessment of anaphylaxis as an SAE, reference is made to the 2012 FDA Guidance for Industry and Investigators, “Safety Reporting Requirements for INDs and BA/BE Studies,” that states, “An adverse event or suspected adverse reaction is considered “life-threatening” if, in the view of either the investigator or sponsor, its occurrence places the subject or subject at immediate risk of death. It does not include an adverse event or SAR that, had it occurred in a more severe form, might have caused death.” Thus, for the reporting of anaphylaxis as an SAE, the severity of the reaction, assessed according to the EAACI system for grading the severity of anaphylactic reactions (Muraro 2007), is also to be taken into account (see **Table 5**).

When the diagnosis of anaphylaxis is made, the basis for having suspected the diagnosis must be documented, using the criteria detailed above.

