11.3. Grading and Attribution of Adverse Events

11.3.1. Grading Criteria

The study site will grade the severity of all allergic and non-allergic adverse events, experienced by the study subjects according to the criteria set forth in the National Cancer Institute's Common Terminology Criteria for Adverse Events (CTCAE) Version 5.0. This document (referred to herein as the NCI-CTCAE manual) provides a common language to describe levels of severity, to analyze and interpret data, and to articulate the clinical significance of all adverse events. The NCI-CTCAE has been reviewed by the Principal Investigator and has been deemed appropriate for the subject population to be studied in this protocol. For additional information and a printable version of the NCI-CTCAE manual, consult the NCI-CTCAE web site:

https://ctep.cancer.gov/protocoldevelopment/electronic_applications/docs/CTCAE_v5_Quick_Reference_5x7.pdf

Adverse events will be graded on a scale from 1 to 5 according to the following standards in the NCI-CTCAE manual Events Grade 1 or higher will be recorded on the appropriate AE paper CRF for this study.

Grade 1 = mild adverse event

Grade 2 = moderate adverse event

Grade 3 = severe and undesirable adverse event

Grade 4 = life-threatening or disabling adverse event

Grade 5 = death

In the case that the diagnosis of anaphylaxis is made, the severity of the anaphylactic event will be assessed and staged according to the EAACI system for grading the severity of anaphylactic reactions ([Muraro 2007](#)) detailed in **Table 5**.

Table 5. Criteria for Grading of Anaphylaxis Severity

Staging System of Severity of Anaphylaxis	
Stage	Defined By
1. Mild (skin & subcutaneous tissues, GI, &/or mild respiratory)	Flushing, urticaria, periorbital or facial angioedema; mild dyspnea, wheeze or upper respiratory symptoms; mild abdominal pain and/or emesis
2. Moderate (mild symptoms + features suggesting moderate respiratory, cardiovascular or GI)	Marked dysphagia, hoarseness and/or stridor; shortness of breath, wheezing & retractions; crampy abdominal pain, recurrent vomiting and/or diarrhea; and/or mild dizziness
3. Severe (hypoxia, hypotension, or neurological compromise) (i.e. Life threatening)	Cyanosis or SpO ₂ ≤ 92% at any stage, hypotension, confusion, collapse, loss of consciousness; or incontinence

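### Section 10.3 counts hypotension after milk dosing or challenge but not neurological compromise, so some Stage 3 anaphylaxis meets no listed pause at any count

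*Combined protocol and SAP*

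**What the plan says.** Section 10.3, repeated in the synopsis, lists events on which "study enrollment will be suspended, the initial dose day will be suspended, dose escalation during build-up will be paused", with enrolled participants held at their current dose until the data are reviewed. The triggers that a milk reaction could meet are:

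- a death related to dosing;
- one case of severe, prolonged anaphylaxis at OIT or a challenge that fails three doses of epinephrine or involves intubation;
- for low blood pressure, "More than 2 cases of hypotension related to milk OIT or oral food challenge";
- a count above three of events of the type "Severe adverse event, other than anaphylaxis, related to investigational product";
- for repeated injections, "More than 3 participants require more than 2 injections of epinephrine for anaphylaxis during a single dosing event of milk OIT".

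Section 10.1 governs the individual. Among its grounds for ending participation are "Anaphylaxis resulting in hypotension, neurological compromise or mechanical ventilation secondary to OIT dosing or any food challenge" and aggressive treatment such as "three or more doses of epinephrine for a life threatening reaction".

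Table 5 in Section 11.3.1 defines Stage 3 as "Severe (hypoxia, hypotension, or neurological compromise) (i.e. Life threatening".

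**The concern.** Section 10.1 acts on the person who reacted. It does not add up events across participants or hold escalation for the others, some of whom may be 4 years old. That is the purpose of Section 10.3, which carries over hypotension and intubation from Section 10.1 but not neurological compromise, and gives no reason. Anaphylaxis is also taken out of the severe-event count, so the omitted case is not picked up there.

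Followed as written, a run of children who lose consciousness after a milk dose and recover with one or two epinephrine injections would meet no listed pause, provided none had hypotension. Three hypotensive participants given one injection each would. Whether anyone acted on the first pattern would depend on discretion.

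**Working it through.** **1. Which severe features are counted**

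| Feature | Table 5, Stage 3 | Section 10.1 (individual) | Section 10.3 (trial) |
|---|---|---|---|
| Hypotension | yes | yes | pause at the third case |
| Neurological compromise | yes | yes | not counted |
| Hypoxia | yes | not listed | not counted |
| Ventilation / intubation | not listed | yes | pause at the first case (intubation) |

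**2. Applying the Section 10.3 triggers.** Take reactions diagnosed as Stage 3 anaphylaxis through hypoxia or neurological compromise, without hypotension, intubation or death, each in a different participant. I checked 1, 3, 4, 20 and 116 such cases.

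| Setting | Epinephrine | Listed pause |
|---|---|---|
| OIT | 0 to 2 doses, responds | none at any count |
| OIT | 3 doses, responds | from the fourth participant |
| Challenge | 0 to 2 doses, responds | none at any count |
| Challenge | 3 doses, responds | none if the injection trigger excludes challenges; from the fourth participant if it includes them |
| Either | no response to 3 doses | first case |

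The third-dose challenge row is open because the injection trigger names milk OIT only. The two neighbouring triggers name both OIT and challenges, which suggests exclusion, but Table 2 labels the challenge doses as milk OIT doses. The separate trigger on epinephrine at a dupilumab injection needs more than two injections and is tied to the drug, so it does not help.

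**3. How often this might arise.** The protocol states no operating characteristics for these rules. Its only rate is below 0.1% for life-threatening anaphylaxis (Sections 5.3 and 5.7), without a denominator. Section 13.2 gives 116 enrolled and 88 after drop-out. Each participant has one milk challenge at screening, week 18 and week 24.

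- With drop-out: 116 + 2 × 88 = 292 milk challenges.
- Without drop-out: 3 × 116 = 348.

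Expected events = np; P(at least 1) = 1 − (1 − p)^n; P(at least 3) is the binomial upper tail. At p = 0.001:

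| Assumed denominator | n | Expected | P(≥1) | P(≥3) |
|---|---|---|---|---|
| Participants | 116 | 0.116 | 0.110 | 0.0002 |
| Challenges, with drop-out | 292 | 0.292 | 0.253 | 0.0033 |
| Challenges, no drop-out | 348 | 0.348 | 0.294 | 0.0054 |

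Table 5 also counts any SpO2 at or below 92%, which may be commoner than the quoted rate. If every Stage 3 event counted towards the more-than-two rule, P(≥3) for n = 292 and 348 would be 0.059 and 0.088 at an assumed 0.3%, 0.181 and 0.253 at 0.5%, and 0.560 and 0.677 at 1%. OIT doses add exposure for which no rate is given.

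**4. Timing.** Section 12.2 schedules DSMB meetings every 6 to 12 months. Six months is about 26 weeks, longer than one participant's 24-week course, so a whole course with both 4040 mg challenges can fall between scheduled meetings.

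**5. Cost of a pause.** From a 20 mg start, Table 1 needs six steps to 1000 mg (40, 80, 160, 320, 640, 1000), and Visits 5 to 10 are six visits. One lost step leaves 640 mg at Visit 10.

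**The case against.** The other side has real weight. OIT and challenges are expected to cause reactions, so thresholds based on response to treatment are defensible. Section 10.3 opens with general authority for the investigator or DSMB to act, the DSMB can meet early (12.2), and the sponsor can terminate for safety (12.5). Life-threatening anaphylaxis is an event of special interest reported to the sponsor within 24 hours (11.2.5, 11.5). The gap bites only if nobody uses these routes. All of this stands, but none of it is a count or an automatic pause.

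A reader might infer more than the documents support:

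- *That every hypoxic or neurological reaction escapes.* Only those diagnosed as anaphylaxis do. Under Section 11.2.6, respiratory compromise alone does not meet the first two sets of criteria. A severe single-system reaction recorded as a related adverse event can count under the severe-event trigger.
- *That all neurological cases are missed.* Section 11.2.6 links syncope, hypotonia and incontinence to reduced blood pressure. Some such cases will also have hypotension and already count.
- *That adding hypoxia to the count merely aligns 10.3 with 10.1.* Section 10.1 does not list hypoxia. A count-based pause for it would be a new rule and a trade-off.
- *That the three-dose limit at challenges is settled.* It rests on the ambiguous wording noted above.
- *That oversight is absent.* The DSMB charter (5.8.1) and Manual of Procedures are not in the documents and may contain these triggers.

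Section 11.2.1 records expected reactions within two hours as dosing reactions, not adverse events, with a stated exception only for home dosing. Life-threatening reactions should still be reported under the serious and special-interest rules, but this makes an explicit route to the DSMB more useful.

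**Conclusion.** The concern holds in a limited form. Among reactions diagnosed as Stage 3 anaphylaxis, neurological compromise and hypoxia have no trial-level count of their own. Without hypotension, intubation or death, and with response to two or fewer epinephrine doses, such reactions meet no listed pause at OIT at any count. At a challenge the limit is two or three doses, depending on how the injection trigger is read. Neurological compromise is a true mismatch between Sections 10.1 and 10.3. Hypoxia is a gap against Table 5 only.

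The events should be rare: about 0.1 to 0.35 expected at the 0.1% ceiling, depending on the assumed denominator, with OIT doses extra. These figures show that a wider rule would seldom act. They do not measure harm avoided, and the higher rates in the working are assumptions. The case for change is that the affected events are life-threatening, the existing routes are individual, reporting-only or discretionary, and the correction is small. Confidence is moderate because the DSMB charter and Manual of Procedures could not be checked.

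**What to change.** Amend Section 10.3 and the synopsis in the same way:

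1. Widen the hypotension trigger to more than two cases of either hypotension or anaphylaxis with neurological compromise, for milk OIT and food challenges alike.
2. Require prompt DSMB review of each Stage 3 (life-threatening) anaphylaxis related to milk OIT or a food challenge. This covers hypoxic cases without a new count-based pause, which a brief fall in SpO2 could otherwise set off. Say whether Stage 3 means Table 5 as printed or the narrower test in Section 11.2.6, that "its occurrence places the subject or subject at immediate risk of death".

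If the DSMB charter or Manual of Procedures already contains these triggers, a cross-reference is enough. The same amendment could usefully state whether the injection trigger covers challenges and whether pending challenges are held during a pause; these are clarifications.

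The cost is one edited bullet and a few added sentences. Anaphylaxis is already staged and life-threatening cases are already reported within 24 hours, so no new data are needed. The DSMB gains a little work, and a pause becomes slightly more likely. A pause could delay an up-dosing step before week 18. Section 13.5.1 counts a missing week 18 result as non-response, so the amendment should say that held challenges are done late rather than skipped.

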5.7. DBPCFC Safety Considerations

Oral food challenges may induce an allergic response. Allergic reactions can be severe, including life-threatening allergic reactions; however, the risk of an allergic reaction is reduced by initiating the challenge with a very small amount of the food, gradually increasing the dose, and closely monitoring for signs of prespecified challenge-stopping symptoms. If subjects have an allergic reaction during the challenges, they may need oral, IM, or intravenous (IV) medications. Subjects will have an IV catheter placed before the food challenges if they have a medically documented history of anaphylaxis with hypotension requiring IV fluid resuscitation. Additionally, IV catheters may be placed, at clinician discretion for any visit, based on factors such as previous reactions, recent clinical history, and clinical status observed at the visit. Trained personnel, as well as medications and equipment, will be immediately available to treat any reaction. The anticipated rate of life threatening anaphylactic reactions is <0.1%.

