5.8. Study Committees

5.8.1. Data and Safety Monitoring Board

The ongoing Stanford Food Allergy DSMB, independent from the study investigators, will provide oversight of subject safety by conducting formal reviews of accumulated safety data that will be blinded by treatment group. If requested, the DSMB may have access to the treatment allocation code or any other requested data for the purposes of a risk-benefit

assessment. The DSMB currently provides the Sean N Parker Center for Allergy & Asthma Research with appropriate recommendations on the conduct of the Food Allergy, Asthma, Atopic Dermatitis, Nasal Polyposis and EoE clinical studies to ensure the protection and safety of the subjects enrolled in these studies. All activities and responsibilities of the DSMB are described in the DSMB charter.

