As detailed above, the subject will have a physical examination and lung function assessment conducted to ensure it is safe and appropriate to proceed with the escalation. Vital signs will be assessed every 15 minutes. Each DBPCFC will consist of 7 doses (milk protein or placebo), given every 15 to 30 minutes: 10 mg, 30 mg, 100 mg, 300 mg, 600 mg, 1000 mg, and 2000 mg protein, resulting in a total challenge of up to 4040 mg milk protein (cumulative). If the study team suspects a reaction may be developing, they may exercise their clinical judgment to separate doses by up to an additional 30 minutes (1 hour maximum between doses). The food challenge will be stopped and appropriately treated in the occurrence of two or more objective Grade 1 (Mild) reactions involving two or more organ systems; OR a persistent Grade 1 (Mild) reaction; OR any reaction of Grade 2 (Moderate) or higher severity. The subject's tolerance to milk allergen, or cumulative tolerated dose (CTD), is defined as the highest cumulative protein dose in which the subject does not experience any of the dose-limiting symptom criteria listed above. After the last dose of each DBPCFC, the subject will be monitored for a minimum of 2 hours and then discharged from the clinic only when deemed clinically stable by a study clinician. The food challenges can be performed on consecutive days if no reactions have occurred. If a reaction occurs and is treated, then the challenges should be at least 48 hours apart.

Participants will be discharged with a new kit of home OIT doses at Visit 11a at the same dose as that previously dispensed and tolerated at Visit 10. Participants will skip their daily home dose of milk OIT on DBPCFC days (Visit 11a and b), but will take their home dose on days between the DBPCFCs if the DBPCFCs are not on consecutive days.

Washout Phase (Non-DBPCFC Visits: Visits 12 and 13)

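### The epinephrine-count stopping trigger names milk OIT only, so week-18 or week-24 challenge anaphylaxis that responds by the third injection is never counted; one added phrase would close this gap

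*Combined protocol and SAP*

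**What the plan says.** Section 10.3 (Study Stopping Rules) and the matching synopsis row list seven numeric triggers. Meeting any of them suspends enrollment and the initial dose day, pauses build-up escalation, and means that "all enrolled participants will remain on their current dose pending expedited review of all pertinent data".

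Four of the triggers matter most here:

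- Refractory anaphylaxis, triggered by a single case: "One case of severe and prolonged anaphylaxis related to milk OIT dosing or oral food challenge that does not respond to 3 doses of epinephrine". A case with intubation also qualifies.
- Hypotension: "More than 2 cases of hypotension related to milk OIT or oral food challenge".
- Epinephrine count: "More than 3 participants require more than 2 injections of epinephrine for anaphylaxis during a single dosing event of milk OIT".
- Severe adverse events, triggered by more than three: "Severe adverse event, other than anaphylaxis, related to investigational product".

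The other three are a dosing-related death, a separate epinephrine count tied to a dupilumab injection, and more than three cases of biopsy-confirmed symptomatic eosinophilic esophagitis. Section 10.3 also has a non-numeric clause under which the investigator or DSMB may act on conditions they consider serious enough to stop the study.

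Section 8.3 sets the week-18 and week-24 challenges at up to 4040 mg cumulative milk protein, against a maximum daily OIT dose of 1000 mg. A challenge stops at two or more objective mild reactions in two or more organ systems, or at "a persistent Grade 1 (Mild) reaction; OR any reaction of Grade 2 (Moderate) or higher severity".

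**The concern.** Two of the three triggers for milk-induced anaphylaxis name both ways of being exposed to milk in this trial, daily OIT and the food challenge. The epinephrine count names only the first. The severe-adverse-event trigger does not pick up the remainder, because it sets anaphylaxis aside.

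A third injection is well past the point at which a challenge is meant to end. Four participants who each need three injections during OIT dosing would bring a pause and an expedited review by rule. The same four at their week-18 or week-24 challenges, where the cumulative dose can be about four times the top daily dose (4040 / 1000 = 4.04), would not. The trial enrolls children from age 4, so a written count for the higher-dose exposure is worth having.

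**Working it through.** **Step 1. Run one case through all seven triggers.** The case is anaphylaxis at a week-18 or week-24 challenge, three epinephrine injections, response by the third, no hypotension, no intubation, no death.

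| Trigger (Section 10.3) | Met? | Reason |
|---|---|---|
| Dosing-related death | No | Participant survives |
| Epinephrine count, dupilumab injection | No | Last injection is at week 16 (8.3) |
| Refractory or intubated anaphylaxis | No | Responds by the third dose, no intubation |
| Hypotension | No | None occurs |
| Epinephrine count, milk OIT | No | Challenge not named |
| Severe adverse event | No | Anaphylaxis excluded |
| Eosinophilic esophagitis | No | Different condition |

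The result is 0 of 7, and repeating the case in more participants does not change it.

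**Step 2. Can milk OIT be read to include the challenge?** Table 2 heads its challenge-dose columns as milk OIT/placebo doses, which gives that reading some footing. Against it, the home OIT dose is skipped on challenge days (8.3), and Table 4 marks no OIT administration at Visits 11a, 11b, 14a or 14b. If milk OIT already included challenges, naming challenges in the two neighbouring triggers would be redundant.

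**Step 3. Bound the class.** A severe and prolonged reaction that needs a fourth injection has not responded to three, so it triggers review as a single case. The uncounted class is therefore mainly exactly three injections with response, plus any longer course not judged severe and prolonged. Hypotensive cases count towards the hypotension trigger. Death at a challenge is arguably covered, since the death trigger speaks of dosing without naming challenges.

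**Step 4. Other provisions that reach this class.**

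- 10.1: individual discontinuation after three or more doses, worded for a life-threatening reaction.
- 11.2.5 with 11.5: life-threatening anaphylaxis is an event of special interest, reported within 24 hours. Table 5 equates life-threatening with hypoxia, hypotension or neurological compromise, so a moderate-stage reaction treated with three injections may fall outside.
- 11.2.1: expected, related challenge reactions within two hours are recorded as dosing reactions, not AEs. The Grade 3 exception is written for home dosing.
- 12.2: DSMB meetings every 6 to 12 months, or earlier if needed.

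None of these sets a count.

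**Step 5. How often could four occur?** The plan gives no rate for needing more than two injections at a challenge, so the rates below are assumptions. The number of participants is 88, the 44 + 44 of Section 13.2, taken as those challenged at week 18. With X binomial(88, p):

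P(X ≥ 4) = 1 − Σ (k = 0 to 3) C(88, k) p^k (1 − p)^(88 − k)

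| Assumed rate p | Expected count 88p | P(X ≥ 4) |
|---|---|---|
| 0.1% | 0.088 | <0.00001 |
| 1% | 0.88 | 0.012 |
| 2% | 1.76 | 0.100 |
| 5% | 4.4 | 0.647 |

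The 1% to 5% rows are upper bounds for the uncounted class, because they include hypotensive, refractory and intubated cases that other triggers pick up. If half the cases fall in the class (p = 0.5%, 1%, 2.5%), the probabilities are 0.001, 0.012 and 0.179.

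The 0.1% row uses the only challenge figure in the plan: "The anticipated rate of life threatening anaphylactic reactions is <0.1" percent (Section 5.7). That describes a different event. Week-24 challenges would add cases and are not included.

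**The case against.** The best counter-argument is that the omission is deliberate. A challenge escalates under supervision until a reaction or the top dose, staff have standing orders to give epinephrine promptly (5.5), and 11.2.4 says that epinephrine given to stop a non-life-threatening challenge reaction from progressing does not make it an SAE. On that view an injection count is a poor alarm at a challenge, and Section 10.3 rightly relies on outcomes there: refractory course, intubation, hypotension.

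Part of this stands, since some epinephrine use at challenges is expected. But 11.2.4 deals only with SAE classification and gives no reason for leaving challenges out of the count. The threshold is also far above routine use: more than two injections in more than three participants. Reactions are expected during OIT too (up to 95% of subjects, Section 5.3), and the count applies there.

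The second argument is that other controls exist. They do, and the DSMB charter may hold numeric alerts: "All activities and responsibilities of the DSMB are described in the DSMB charter". The charter is not among the documents, so the point is limited to what the protocol itself sets.

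The third is that the probabilities rest on invented rates. That is correct; they show only how strongly the answer depends on an unknown rate.

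The fourth is that the pause might not address the hazard. The listed actions concern enrollment, the initial dose day, escalation and the current OIT dose. A reader might take holding the current dose to mean that challenges stop as well, but the text does not say so. This stands, and the fix deals with it.

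**Conclusion.** The gap exists on the wording of Section 10.3 and the synopsis, and closing it is a cheap safety improvement. It covers post-treatment challenge anaphylaxis treated with three injections that responds by the third, without hypotension, intubation or death, plus longer courses not judged severe and prolonged. No numeric study-level trigger counts that class.

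Stronger readings are not supported. A reader might infer that challenge anaphylaxis in general escapes the stopping rules; refractory, intubated and hypotensive cases are explicitly included. A reader might infer that nobody could act on such cases; the investigator and DSMB can, at their discretion. A reader might infer that four such cases are likely; the documents give no rate, and the illustrative probabilities run from near zero to 65%, the latter an upper bound at an assumed 5%. Nor do the documents show whether the omission is an oversight or a choice.

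The conclusion rests on reading milk OIT in the trigger as separate from the challenge, which the neighbouring bullets and the skipped home dose favour. It does not affect the primary analysis or the sample size.

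**What to change.** In Section 10.3 and the synopsis, extend the epinephrine-count bullet after the words milk OIT with: *or a week-18 or week-24 oral food challenge*. Keep a single pooled count of more than three participants, as the hypotension trigger already pools both exposures, and let it prompt the same expedited review. Screening challenges can stay out, since they precede treatment.

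In the same edit, state whether pending week-18 and week-24 challenges are held during the review. Without that sentence, the rule could pause OIT escalation because of challenge reactions while challenges go on.

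The cost is one phrase in two places and one sentence on pending challenges, with no change to Section 13. The downside is a somewhat higher chance of a temporary pause (a review, not termination). If challenges are held, some week-18 primary-endpoint challenges could be delayed, so the sentence should also say how a delayed week-18 challenge is handled.
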